PROTOCOL N ° 2

Title: Quantitative assessment of the activation of brain areas with positive and negative emotional stimuli and its correlation with degrees of emotional disorder.

NCT number: not yet assigned

Document date: 06/01/2021

Updated: 10/11/2021

INCOR IMAGES - [name]

Main investigator: [name] Head of Magnetic Resonance Imaging at Incor Images.
[contact] [contact]

Collaborators: Graduates in production of Bioimages [name], [name] and [name] from the Magnetic Resonance Imaging Area of Incor Images.

REFERENTIAL FRAME

The technology applied in functional magnetic resonance imaging allows us to visualize on a color scale the changes in the blood flow of those sectors of the brain that increase their metabolic activity during a given action. This is achieved by mapping the volume of cerebral blood, known by its acronym in English as CBV (cerebral blood volume), which increases or decreases according to the metabolic activity in a certain region of the brain. This indirect method of measuring the metabolic activity of brain areas is very useful for anatomically identifying motor areas and critical functions in individual patients prior to neurosurgery, to allow better surgical planning. Currently this is its main application in healthcare practice. In the field of research it is applied in clinical neurology, psychiatry and psychology. Studies have been conducted on the activations of brain regions in basic emotions. There is less data on the quantitative differences of these activations in the Argentine population according to the degree of emotional disorder, this being the object of study of this project.

JUSTIFICATION

By comparing the findings of clinically of participants with different degrees of emotional disorder, treatment strategies can be developed based on the functional findings obtained.

PROBLEM STATEMENT

The diversity of feelings derived from basic emotions and the many possible combinations of their effects in emotional disorders, may mean that generic treatments for different clinical syndromes do not have the same efficacy in all patients. A more detailed study of the type and magnitude of brain activation related to the degree of emotional disorder will allow the development of personalized treatment strategies focused on obtaining better therapeutic results.

RESEARCH QUESTION

Are there differences in the activation of brain areas with positive and negative emotional stimuli that are related to the degree of emotional disorder that can be used in symptomatic patients to develop personalized treatment strategies?

GENERAL AND SPECIFIC OBJECTIVE

The general objective is to demonstrate the relationship between the activation of brain areas and its intensity with the degree of emotional disturbance. In turn, the recognized patterns will be compared with the different degrees of emotional disorder determined by a validated survey, to try to determine the weight of the emotional disorder on each type of activation according to the stimulus received as a specific objective on each one of them in particular.

HYPOTHESIS

The activation of specific brain areas follows common patterns for basic emotions and their derived feelings depending on whether they are positive or negative emotions, while in patients with emotional deficits the activation patterns are different and this difference can manifest itself in specific emotions.

METHODOLOGY TYPE OF STUDY

Initial exploratory, observational, cross-sectional study.

UNIVERSE

Population of the City of La Rioja.

SAMPLE

We estimate that 13 participants would give the study more than 80% power to detect a change between measures of 5% or more, using a linear mixed model for repeated measures, with a type I error of 5% (3).

INCLUSION, EXCLUSION AND ELIMINATION CRITERIA

Volunteers who express their informed consent to participate in the research protocol will be included. The exclusion criteria will be the impossibility of the patient to actively collaborate with the tests to be carried out for the measurement of emotional responses and / or the conditions that represent contraindications for carrying out MRI studies in general. The elimination criterion will be the appearance of any of the two exclusion criteria mentioned at any time during the development of the research.

OPERATIONALIZATION OF VARIABLES

Variable: increased metabolism of a brain area before the application of an emotional stimulus. The stimuli will be generated by paradigms designed to generate positive and negative emotional responses, using audiovisual material constituted by fragments of films validated for the local population (9), following in all cases the quality requirements of paradigms defined by the American Society of Functional Neuroradiology (ASFNR).

Type of variable: dependent, controlled.

Origin of the variable: attributive.

Operational definition: the increase in metabolism in a given brain area is indirectly quantified through mapping the brain blood volume in that area in relation to a stimulus. Indicator: The comparative mapping will be the input to determine the indicator in the comparative assessment of patients according to their score in the variable on emotional disorders. Measurement level: ratio or proportion.

Variable: The categorization of the volunteers by score for levels of emotional disturbance using the 37-question version of the CESIM, validated for the local population (10).

MEASUREMENT TOOLS

Philips Prodiva resonator, year of manufacture 2018, with 1.5 Tesla magnetic field, BOLD sequence, for the measurement of blood flow variations as an indirect parameter of the metabolic activation of specific brain areas, post-processing software incorporated in the resonator, sound circuit compatible with the resonance room for auditory stimuli and external projection of images with mirror system for visual stimuli.

INFORMATION ACQUISITION

The training of Graduates in Production of Bioimages for the application of the fMRI paradigms will be in charge of the principal investigator. The design of the paradigms will be carried out by the principal investigator. At the time of the study, the acquisitions during the implementation of the paradigms will be made by the Graduates in Bioimagenes Production under the supervision of the researchers. The CESIM 37 questionnaires will be filled out by the participants prior to obtaining the fMRI images.

The technical parameters in the acquisition of the fMRI images will be the following: Volumetric acquisition in T1 will be made with a 1.2 mm slice thickness without gap, with TR 7000.0 and TE 154.9.

Two BOLD acquisitions will be made, the first with a positive stimulus and the second with a negative stimulus, obtaining in each one the slices with a 4 mm slice thickness without gap, TR 3000.0 and TE 50.0

The positive and negative paradigms have duration of 250 seconds each, with an initial rest period of 80 seconds, a validated video projection for 140 seconds and a final rest period of 30 seconds for the positive stimulus and 80-130-40 seconds for the negative stimulus.

STATISTICAL ANALYSIS PROGRAM

The final data processing will be carried out with statistical tools to quantitatively compare the activation areas in the different clinical scenarios according to the type of stimulus administered. The activation areas before the positive and negative stimulus will be quantified in cm³ and fMRI Z-score and correlated with the score of the emotional questionnaire. Pierson's correlation coefficient will be used for data of normal distribution or Spearman in case of not having normal distribution.

PLAN FOR THE PRESENTATION OF THE INFORMATION

Starting on July 1, 2021, it is planned to provide the Committee with information on the progress of the project every 30 days, namely on 8/1, 9/1, 10/1 and 11/1, 2021 to later present the final report.

SCHEDULE OF ACTIVITIES

Calibration and fine-tuning of the enabled software and tests in healthy volunteers of the auditory and visual paradigms developed by the researchers. From 7/1/21 to 7/25/21. fMRI sessions for the quantification of emotions in different parameters with healthy volunteers. From 7/28/21 to 10/30/21.

Statistical post-processing of results from 11/01/21 to 11/22/21. Presentation of the final report on 11/30/21 and subsequent submission to a scientific journal for consideration of its publication.

BUDGET

The use of the BOLD sequence to perform fMRI is provided free of charge by Philips for a limited period of time for the purposes of carrying out this research protocol. No disposables or medications are used. The necessary elements for the construction of paradigms, stationery, etc. they will be contributed by the researchers. No expenses are generated for

Incor, except for the use of the room, light, etc., during the MRI acquisitions that will be carried out at specific times without interfering with the healthcare task.

ETHICAL CONSIDERATIONS

The informed consent of each volunteer participant will be requested, including a personal interview to clarify any doubts that may arise and explain in detail and clearly the characteristics of the study. Attached is a letter of adherence to the 2013 Declaration of Helsinki. The researcher's Certificate of Ethics issued by the La Rioja Council of Physicians is attached. The protocol is presented for evaluation by INCOR's Ethics Committee.

BIBLIOGRAPHY

1-Ríos, M. Neurosychology and Functional Magnetic Resonance. Radiology. Volume 50, Issue 5, October 2008 , , pages 351-365. doi: 10.1016 / S0033-8338 (08) 76050-8

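### The claimed power of over 80% with 13 participants is for a change between repeated measures; the planned correlation with the CESIM score reaches 80% only at |r| of about 0.7

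*Protocol*

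**What the plan says.** **Sample size.** The Sample section of the protocol states: "We estimate that 13 participants would give the study more than 80% power to detect a change between measures of 5% or more". The sentence goes on to name a linear mixed model and a 5% type I error, and cites reference 3. It gives no standard deviation, no within-person correlation and no sidedness.

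**Objective.** The General and Specific Objective section states: "The general objective is to demonstrate the relationship between the activation of brain areas and its intensity with the degree of emotional disturbance". The protocol title likewise speaks of correlation with degrees of emotional disorder.

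**Data per participant.** Under Information Acquisition: "Two BOLD acquisitions will be made, the first with a positive stimulus and the second with a negative stimulus". In the same section: "The CESIM 37 questionnaires will be filled out by the participants prior to obtaining the fMRI images". No repeat of the questionnaire is described.

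**Analysis.** The Statistical Analysis Program section says that the activation areas under each stimulus "will be quantified in cm³ and fMRI Z-score and correlated with the score of the emotional questionnaire", and then: "Pierson's correlation coefficient will be used for data of normal distribution or Spearman in case of not having normal distribution". It also announces a comparison of activation by clinical scenario and type of stimulus, but names no method for it. The mixed model does not appear in this section, and no detectable correlation is given anywhere in the protocol.

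**The concern.** The sample size rests on one quantity and the main analysis on another. A change between repeated measures is a contrast among scans, most naturally positive against negative stimulus in the same person. The correlation with CESIM asks whether people with higher scores activate more or less than people with lower scores. It has 13 pairs of values and no repeated-measures contrast, so power for the first says nothing about power for the second.

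A reader who sees a claim of over 80% power will attach it to the stated objective. A non-significant correlation would then tend to be read as showing no relationship, when the study had little chance of detecting a moderate one.

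**Working it through.** **Inputs from the protocol:** n = 13; target power above 80%; effect of 5% or more; type I error 5%; two scans and one CESIM score per participant; Pearson or Spearman as the test.

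**Assumptions:** two-sided testing; bivariate normality for Pearson; the 5% change and its SD expressed in the same percentage-point units.

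**1. The protocol's own figure.** It cannot be reproduced, because no SD is given. What can be found is the SD it would need. With two measures per person the mixed model reduces to a paired comparison with 12 degrees of freedom and noncentrality d × √13, where d is the mean change divided by the SD of the differences.

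- Power of 80% (exact noncentral t, two-sided) requires d = 0.847.
- A 5-point change therefore needs an SD of differences of at most 5 / 0.847 = 5.9 points. A one-sided test would allow 5 / 0.732 = 6.8.

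| SD of differences, points (assumed) | Two-sided power for a 5-point change |
|---|---|
| 5 | 91% |
| 5.9 | 80% |
| 7.5 | 60% |
| 10 | 38% |
| 15 | 20% |

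The claim may be true for this contrast, but the protocol does not let anyone check it.

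**2. The planned correlation.** The two-sided 5% critical t on 11 degrees of freedom is 2.201, so the critical |r| = 2.201 / √(11 + 2.201²) = 0.553.

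Power was simulated from bivariate normal data (400,000 replicates per value of r). The number needed for 80% power is from Fisher's z, n = ((1.96 + 0.8416) / atanh r)² + 3, rounded up.

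| True r | Power at n = 13 | n for 80% power |
|---|---|---|
| 0.3 | 17% | 85 |
| 0.4 | 28% | 47 |
| 0.5 | 43% | 30 |
| 0.6 | about 63% | 20 |
| 0.69 | 80% | – |

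Fisher's z gives the detectable correlation directly: tanh((1.96 + 0.8416) / √10) = 0.709. Simulation and approximation thus agree on 0.69 to 0.71.

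**3. Precision.** For an observed r of 0.5 the 95% interval is tanh(0.549 ± 1.96 / √10), that is, tanh(−0.070) to tanh(1.169), or −0.07 to 0.82.

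**4. Sensitivity of the 0.7 figure.**

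- Spearman, with an assumed variance factor of 1.06: tanh(2.8016 × √(1.06 / 10)) = 0.72.
- One-sided Pearson: about 0.64 to 0.66.
- Two activation measures under two stimuli make at least four correlations. If Bonferroni were applied over four (two-sided level 0.0125, z = 2.498), the detectable value is tanh((2.498 + 0.8416) / √10) = 0.78.

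**The case against.** The strongest reply is that the power sentence is not shown to be false. It cites a reference that may supply the variability, and it has a possible home in the design: each person is scanned under two stimuli, the research question asks about differences with positive and negative stimuli, and the statistical section plans a comparison by stimulus type. A mixed model could serve that comparison, and one with CESIM as a covariate could even address the objective. The study also calls itself exploratory, has no decision rule, and nowhere says that a null correlation will be taken as no relationship.

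Part of this stands. The figure of over 80% is not shown to be miscalculated for the stimulus contrast, and reading the change as within-person is an inference from the repeated-measures wording. Exploratory status also softens the consequence. It is fair to add that a single figure of about 0.70 is the favourable case, given several correlations and a possible Spearman test.

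The mismatch remains. The protocol never says that CESIM enters a mixed model, and even then a 5% change between measures would not be an effect size for the association with CESIM. The only named tests are correlations, and they carry the title and the general objective. Exploratory status would excuse giving no power figure; it does not make a figure for one analysis apply to another.

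**Conclusion.** The concern holds. The stated power does not belong to the study's main test, and nothing else in the protocol supplies a figure that does. For one unadjusted two-sided 5% Pearson test, 13 participants give 80% power only at |r| of about 0.7. A true correlation of 0.5 would be missed more often than found (100% − 43% = 57%). Allowing for Spearman or for several correlations moves the detectable value up to about 0.72 to 0.78; a one-sided test would lower it to about 0.65. None of these brings a moderate correlation within reach.

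For the 5% change, the claim is unverifiable rather than wrong: it is true if the SD of differences is 5.9 points or less (two-sided).

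**What to change.** Replace the power sentence in the Sample section with one for the planned test, for example:

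> With 13 participants and a two-sided 5% level, a single Pearson test has 80% power for a correlation of about 0.70 or larger between activation and CESIM score. Smaller correlations are estimated with 95% confidence intervals. A non-significant correlation is not evidence of no relationship.

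Add a note that the figure is unadjusted, and that it is about 0.72 for Spearman and about 0.78 with Bonferroni over four correlations. Keep the 5% statement only as a secondary figure for positive against negative stimulus, with the assumed SD of differences (5.9 points or less) and its source. If 13 was chosen on practical grounds, say so.

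The cost is wording only: no participants are added and the design is unchanged. The stated figure becomes less favourable. If the sponsor instead wants 80% power for a smaller correlation, the numbers in the working apply, for example 30 participants for r = 0.5.

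### The claim of more than 80% power at N=13 is for a change between measures under a mixed model; it does not cover the CESIM correlations, the general objective and only named analysis

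*Protocol*

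**What the plan says.** Three parts of the Protocol bear on this point.

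- **SAMPLE.** The only sample-size justification is that "13 participants would give the study more than 80% power to detect a change between measures of 5% or more". The section adds that this holds "using a linear mixed model for repeated measures, with a type I error of 5" percent. A literature reference is cited. No SD, within-person correlation or expected correlation coefficient is given, and the measures between which the change occurs are not identified.
- **GENERAL AND SPECIFIC OBJECTIVE.** The main aim of the study is to "demonstrate the relationship between the activation of brain areas and its intensity with the degree of emotional disturbance". The specific objective concerns how strongly the degree of disorder bears "on each type of activation according to the stimulus received as a specific objective on each one of them in particular".
- **STATISTICAL ANALYSIS PROGRAM.** Activation under each stimulus is to be "quantified in cm³ and fMRI Z-score and correlated with the score of the emotional questionnaire". The method is that Pearson's "correlation coefficient will be used for data of normal distribution or Spearman in case of not having normal distribution". The section also announces statistical tools to "quantitatively compare the activation areas in the different clinical scenarios according to the type of stimulus administered", but names no method for that comparison. The mixed model appears nowhere outside SAMPLE.

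**The concern.** The analysis that was sized is not named in the analysis section, and the analysis that is named has no stated power. The two answer different questions. A change between measures is a within-person contrast, and its power depends on the change relative to the SD of the within-person difference. A correlation with CESIM is an association across people, and its power depends on the true correlation and the number of people. Neither can be derived from the other.

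The SAMPLE section attaches its figure to the study as a whole. A reader who takes this at face value could treat a non-significant correlation as evidence of no relation, on the very question set as the general objective. At N=13 that inference would be unsafe for any but very strong relations.

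**Working it through.** **Inputs from the Protocol.** N=13, power above 80%, a change of 5% or more, type I error 5% (SAMPLE); two BOLD runs per person, one positive and one negative (INFORMATION ACQUISITION). Sidedness is not stated, so two-sided is assumed. All true correlations and SDs below are assumptions.

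**1. The plan's own figure.** Suppose the change is between two measures per person. The mixed-model contrast then reduces to a paired t-test on 12 df with noncentrality (change / SD of difference) × √13.

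- 80% power needs a standardised change of 0.847.
- For a 5-point change the SD of the difference must be at most 5 / 0.847 = 5.9 points.
- If that SD were 5, 8 or 10 points, power would be 91%, 54% or 38%.

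Without an SD, the claim of more than 80% can be neither reproduced nor refuted.

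**2. Smallest observed correlation that reaches significance.** With 11 df, t(0.975) = 2.201, so |r| must exceed 2.201 / √(11 + 2.201²) = 0.553.

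**3. Power of one correlation at n=13.** By Fisher z, ignoring the negligible opposite tail, power = Φ(atanh(ρ) × √10 − 1.96). For ρ=0.5 this is Φ(0.549 × 3.162 − 1.96) = Φ(−0.223) = 41%. Simulation used 100,000 bivariate normal samples per case:

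| True ρ | Fisher z | Pearson, simulated | Spearman, simulated |
|---|---|---|---|
| 0.3 | 16% | 17% | 14–16% |
| 0.5 | 41% | 44% | 36–38% |
| 0.7 | 78% | 82% | 73% |

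Where a Spearman range is shown, it reflects the critical value used (0.560 or 0.553). The figure at 0.7 uses 0.553.

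**4. Correlation needed for 80% power at n=13.** By Fisher z: tanh((1.96 + 0.842) / √10) = 0.71. Simulation gives about 0.69 for Pearson and about 0.74 for Spearman. A one-sided test would lower the Fisher z figure only to 0.66.

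**5. Sample size for 80% power.** n = ((1.96 + 0.842) / atanh(ρ))² + 3, which is 85 at ρ=0.3 and 30 at ρ=0.5.

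**6. Precision.** For an observed r of 0.5: tanh(0.549 ± 1.96 / √10) = tanh(−0.070) to tanh(1.169), a 95% CI of −0.07 to 0.82.

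**The case against.** The strongest reply has three parts.

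- **The study calls itself initial and exploratory, and no significance rule is set for the correlations.** The 5% error rate belongs to the mixed model. This lowers the stakes, but the same document claims more than 80% power for the study, and the interval in step 6 is just as wide if no test is made.
- **A separate SAP may name the mixed model.** Missing detail would indeed be no finding. The point here is that two statements in one document, which has its own analysis section, do not match.
- **The announced comparison by type of stimulus may be where the mixed model belongs.** This is possible, and the text is compatible with it. It would give the sized analysis a place, but would still give the correlations no power.

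A reader might infer three stronger things that the document does not support.

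- *That N=13 is too small for the change, or that its stated power is false.* No SD is given, so this cannot be shown.
- *That the change between measures must be positive versus negative stimulus.* It could equally be rest versus film within a run, since each run contains both.
- *That the plan is wrong for lacking a test of whether the CESIM relation differs between stimuli.* The question that the Protocol poses ("Are there differences in the activation of brain areas with positive and negative emotional stimuli that are related to the degree of emotional disorder") can be read that way, but that is one reading. The per-stimulus correlations do address both stated objectives. A CESIM-by-stimulus product term would also be a debatable gain: in simulated cases at n=13 its power was as low as 11%, and it rejected in up to 39% of samples where the two correlations were equal but the SDs differed by a factor of 2. It is optional and not part of this point.

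**Conclusion.** The mismatch stands. The power stated in SAMPLE belongs to an analysis that the analysis section does not name, and it does not apply to the correlations that serve the general objective. For those, 13 people give 80% power only if the true correlation is about 0.7 (Pearson) or 0.74 (Spearman). A true correlation of 0.5 would be missed in more than half of such studies. These figures assume a two-sided 5% test, bivariate normal data, all 13 people analysed and no multiplicity adjustment. The power claimed for the change remains unverified, not wrong. Given the exploratory design, this is a clarification that should be made before results are interpreted; it is not a reason to call the design invalid.

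**What to change.** 1. In SAMPLE, state that the power above 80% refers only to the change between measures. Say which measures these are, what the 5% is a percentage of, and which SD of the within-person difference was assumed. Do not present it as power for the correlations.
2. Add that at N=13 the correlation analysis has 80% power only for a true |r| of about 0.7 or more. Report the correlations as exploratory with 95% confidence intervals, and state that a non-significant correlation will not be read as no relation.
3. In STATISTICAL ANALYSIS PROGRAM, name the mixed model for the change it was sized on, or remove it from SAMPLE.

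The cost is wording only, with no new data. The drawback is that the Protocol then shows a less favourable power for its main objective.

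### Does choosing Pearson or Spearman by normality at n = 13 spoil the comparison of the two stimuli, and do four unranked correlations per area need error control?

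*Protocol*

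**What the plan says.** Three parts of the protocol bear on this.

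- **Statistical Analysis Program.** Activation areas under each stimulus are to be "quantified in cm³ and fMRI Z-score and correlated with the score of the emotional questionnaire". The coefficient follows from the distribution: "Pierson's correlation coefficient will be used for data of normal distribution or Spearman in case of not having normal distribution". No normality test is named. The text does not say whether the choice is made once or variable by variable. It gives no p-value or significance threshold for the correlations. What it sets out to compare by type of stimulus is the activation areas.
- **General and Specific Objective.** The overall aim is put as follows: "The general objective is to demonstrate the relationship between the activation of brain areas and its intensity with the degree of emotional disturbance". The specific objective is to try to determine "the weight of the emotional disorder on each type of activation according to the stimulus received", for each of them in particular.
- **Type of Study and Sample.** The study is described as initial, exploratory, observational and cross-sectional. The sample size statement reads "We estimate that 13 participants would give the study more than 80% power". The target is to "detect a change between measures of 5% or more", under a linear mixed model with a 5% type I error.

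**The concern.** Two worries arise.

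**Comparability.** Pearson measures linear association and Spearman measures rank association. A normality check on 13 values is erratic, so chance alone could give an area Pearson for one film and Spearman for the other. If the specific objective is read as a comparison of coefficients across films, part of any difference might then reflect the coefficient and not the brain. On the same 13 pairs at a true r of 0.6, the two coefficients differ by 0.10 or more in 30% to 35% of samples, and fall on opposite sides of p = 0.05 in about 17%.

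**Multiplicity.** Two stimuli times two metrics make four correlations per area. The number of areas is not given and no correlation is named as the main one, while the general objective speaks of demonstrating a relationship. If each were tested at 5%, chance findings would be common.

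**Working it through.** **1. The plan's own figure.** The stated N = 13 cannot be reproduced, because no standard deviation is given. Back-solving a paired comparison (12 degrees of freedom, two-sided 5%), 80% power needs a standardised difference of 0.847. A 5-point change then allows a standard deviation of the differences of at most 5 / 0.847 = 5.9 points. This figure, with its 5% error rate, belongs to the mixed model. It says nothing about the correlations.

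**2. How often would the coefficients differ by stimulus?** Inputs: n = 13 (Sample). Assumptions, since the protocol gives none: Shapiro-Wilk at 5%, applied to each variable including the questionnaire score, and a latent correlation of 0.5 between the two stimuli. Simulation gives:

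| Activation / questionnaire score | Different coefficients |
|---|---|
| normal / normal | 9% |
| gamma(4) / normal | 27% |
| lognormal (0.5) / normal | 40% |
| lognormal (0.5) / lognormal (0.5) | 28% |

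So the event is not rare if the choice is made per variable. The next question is what it does to the comparison.

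**3. Does it create false differences between stimuli?** Take equal true correlations for both films, so that any observed difference is spurious. The standard deviation of the positive-minus-negative difference at r = 0.6 (6,000 runs per case) is:

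| Activation / questionnaire score | Rule as written | Spearman throughout |
|---|---|---|
| normal / normal | 0.238 | 0.257 |
| gamma(4) / normal | 0.241 | 0.252 |
| lognormal / normal | 0.251 | 0.259 |
| lognormal / lognormal | 0.261 | 0.258 |

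At r = 0 the ranges are 0.297 to 0.303 against 0.301 to 0.306. A rough check by hand: with no true correlation, each coefficient has variance about 1/(n − 1) = 1/12, and the covariance of the two is about 0.5/12. The difference then has a standard deviation of about √(2 × (1 − 0.5)/12) = √(1/12) = 0.29. This is the spread that 13 people produce whichever coefficient is used.

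A spurious difference above 0.3 at r = 0.6 occurs in 19% to 24% of studies under the rule and in 22% to 24% with Spearman throughout. Restricted to the samples where the coefficients do differ, the standard deviations are 0.24 to 0.28 against 0.24 to 0.27, so they remain nearly equal. The mean Pearson-minus-Spearman shift in those samples is about 0.00 to 0.03 in the skewed cases, with simulation error of up to about 0.01. It reaches about 0.09 only with normal data, where just 9% of samples are affected.

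**4. Why the effect is small.** For bivariate normal data with r = 0.6, the population Spearman value is (6/π) × arcsin(0.3) = 0.58. The two scales lie about 0.02 apart, against a sampling standard deviation near 0.25.

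**5. What a fixed coefficient would cost or gain.** The rule does not inflate the error of a single test: 4.6% (normal), 5.2% (lognormal) and 4.8% (exponential) at a nominal 5%. Power at r = 0.6 is 61.2% with the rule and 54.4% with Spearman for normal data, a loss of 6.8 points. For lognormal data it is 57.3% and 54.9%, a loss of 2.4 points. Fixing Spearman therefore gives up some power and removes no material spurious difference.

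**6. Multiplicity.** Four independent tests at 5% give 1 − 0.95⁴ = 18.5%. With a correlation of 0.9 between the measures the figure is about 10%. About 50% is reached only by assuming five areas (20 tests) with correlated measures. Each of these numbers needs an unadjusted 5% test of every correlation, which the protocol does not prescribe, and the last also needs an assumed number of areas.

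**The case for a change.** The strongest case for the concern is that it is about estimates and not error rates, so calling the study exploratory does not answer it. The switch is fixed in the protocol itself, and a single sentence would remove the ambiguity. It is true that the wording permits a choice per variable, that the count of four per area is right, and that the discordance rates are real.

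The step from discordance to harm does not stand. Two coefficients computed on the same data can differ by 0.10 and still add nothing visible to a between-stimulus difference that already varies by about 0.25. The simulations give both stimuli the same distributional shape. If one film produced normal activation and the other skewed activation, the shift would run in one direction, but step 4 puts the population gap near 0.02 at r = 0.6, which is again small beside the sampling error.

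The reading behind the concern is also not the only one. The rule can equally mean one choice for all data, and then discordance between stimuli is zero. The specific objective reads naturally as a separate estimate for each stimulus; no contrast of coefficients is stated.

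On multiplicity, the verb in the general objective is stronger than the label exploratory, and the two could be brought into line. That is a matter of wording: the specific objective speaks only of trying to determine, and no inferential claim is attached to the correlations. The normality test, the ranking of metrics and any adjustment are details commonly left to a statistical analysis plan.

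**Conclusion.** The concern does not hold. The rule is a common one, is written down in advance, keeps the single-test error at 4.6% to 5.2%, and leaves the between-stimulus difference as variable as Spearman throughout would (0.24 to 0.26 against 0.25 to 0.26 at r = 0.6). Preferring one coefficient for everything is a matter of taste, with a power cost of 2.4 to 6.8 points in the cases examined. The four correlations per area call for no error control in a study that labels itself exploratory and sets no threshold for them.

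This rests on n = 13, Shapiro-Wilk at 5%, a correlation of 0.5 between stimuli, and normal to moderately skewed data of the same shape under both films. It would need another look if the correlations were later presented as confirmatory tests at 5%.
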